11.2.2 SAEs (Including Deaths) and Adverse Events Leading to Study Drug Discontinuation

Deaths and all SAEs will be presented in listing format. In addition, SAEs and AE leading to study drug discontinuation will be summarized by System Organ Class and MedDRA Preferred Term.

11.3 Analysis of Laboratory Data

Listing and descriptive statistics of laboratory values over time, changes from baseline, and extreme abnormal value on treatment will be provided. Baseline is understood as the last available measurement before risankizumab administration (i.e, BL_RZB defined in Section 6.0). Extreme abnormal value on treatment is understood as the on treatment laboratory value which is most significantly away from the reference range. Frequency of subjects with transitions relative to the toxicity grade according to NCI CTCAE

Version 4.03 and listing of subjects with important abnormal laboratory values will be presented as well.

11.3.1 Variables and Criteria Defining Abnormality

Clinical laboratory tests performed are listed in [Table 13](#).

Table 13. Clinical Laboratory Tests

Category	Test Name
Haematology	Hematocrit (Hct) Hemoglobin (Hb) Glycosylated Hbc (HbA1c) White Blood Cells/Leukocytes Platelet Count/Thrombocytes
Diff. Automatic	Neutrophils (relative count) Eosinophils (relative count) Lymphocytes (relative count)
Enzymes	AST (GOT) ALT (GPT) Alkaline Phosphatase (AP) Creatine Kinase (CK) Gamma-Glutamyl Transferase (GGT/ γ -GT) Lactic Dehydrogenase (LDH) Amylase Lipase
Electrolytes	Calcium Sodium Potassium
Substrates	Glucose BUN (blood urea nitrogen) Uric acid Creatinine eGFR (estimated by CKD-EPI formula) Bilirubin Total Albumin C-Reactive Protein (high sensitive) Cholesterol, total Triglycerides LDL-Cholesterol HDL-Cholesterol
Urinalysis (Stix)	Urine Protein Urine Glucose

11.3.2 Statistical Methods

Analysis of Quantitative Laboratory Parameters (Hematology, Chemistry)

Though the protocol indicates utilizing the Rheumatology Common Toxicity Criteria (RCTC) scale for grading laboratory values, given that the National Cancer Institute Common Toxicity Criteria for Adverse Events (NCI CTCAE) scale includes a more comprehensive list of laboratory values, the sponsor will present the lab analyses based on the NCI CTCAE scale. Changes from Baseline to each scheduled visit and to the final value in continuous laboratory parameters will be summarized with the mean, standard deviation and median. The Baseline (BL_RZB) and visit/final value means will also be presented for subjects who have both the Baseline and visit/final values. If there are multiple post-baseline measurements on the same day, average value will be used.

Shift Tables

Laboratory parameters will be tabulated using shift tables from Baseline to worst values, categorized by the toxicity grade according to NCI CTCAE Version 4.03 of the laboratory used for each sample. A similar shift table will also be provided to summarize shifts from Baseline to the final post-baseline value.

Potentially Clinically Important Laboratory Values

Frequencies and percentages of subjects with post Baseline lab values met the following criteria in [Table 14](#) and [Table 15](#) will be summarized. Of note, a post baseline grade must be more extreme than the baseline grade to be considered a potentially clinically important finding.

Table 14. Criteria for Potentially Clinically Important Chemistry Values

Chemistry Variables	Units	Definition of Potentially Clinically Important Current (Version 4) NCI CTCAE Grade 3 or Greater	
		Very Low	Very High
TBL	mcmol/L		> 3.0 × ULN
SGOT/AST	U/L		> 5.0 × ULN
SGPT/ALT	U/L		> 5.0 × ULN
Albumin	g/L	< 20	
Glucose	mmol/L	< 2.2	> 13.9
Triglycerides	mmol/L		> 5.7
Creatinine	mcmol/L		> 3.0 × ULN (> 3.0 × BL)
Sodium	mmol/L	< 130	> 155
Potassium	mmol/L	< 3.0	> 6.0
Calcium	mmol/L	< 1.75	> 3.1
CPK	U/L		> 5.0 × ULN
Total Cholesterol	mmol/L		> 10.34
GGT			> 5.0 × ULN
ALP			> 5.0 × ULN

Table 15. Criteria for Potentially Clinically Important Hematology Values

Hematology Variables	Units	Definition of Potentially Clinically Important Current (Version 4) Grade 3 or Greater
		Very Low
Hemoglobin	g/dL	< 8.0
Platelets count	10 ⁹ /L	< 50.0
WBC count	10 ⁹ /L	< 2.0
Neutrophils	10 ⁹ /L	< 1.0
Lymphocytes	10 ⁹ /L	< 0.5

A separate listing will be provided that presents all of the subjects and values that are NCI CTCAE toxicity grade 3 or above. For each of these subjects, the whole course of the respective parameter will be listed.

If there are multiple measurements on the same day, the worst value will be used.

Liver Function Tests

The frequencies and percentages of subjects with post baseline liver specific function test values in ALT/SGPT, AST/SGOT, alkaline phosphatase, and total bilirubin will be categorized as follows:

- ALT > 3.0 × ULN
- ALT > 5.0 × ULN
- ALT > 10.0 × ULN
- ALT > 20.0 × ULN
- AST > 3.0 × ULN
- AST > 5.0 × ULN
- AST > 10.0 × ULN
- AST > 20.0 × ULN
- Alkaline phosphatase > 1.5 × ULN
- Total bilirubin > 1.5 × ULN
- Total bilirubin > 2.0 × ULN
- ALT and/or AST > 3× ULN and Total bilirubin > 1.5× ULN
- ALT and/or AST > 3× ULN and Total bilirubin > 2× ULN
- ALT > 3× ULN and Total bilirubin > 1.5× ULN
- ALT > 3× ULN and Total bilirubin > 2× ULN

The listing will include all subjects who met any of the following four criteria:

- ALT > 3 × ULN, or
- AST > 3 × ULN, or
- ALP > 1.5 × ULN, or
- Total bilirubin > 1.5 × ULN.

A listing of possible Hy's Law cases, defined as those who meet all of the following conditions will be provided.

- ALT of $> 3 \times \text{ULN}$ or AST of $> 3 \times \text{ULN}$,
- Total bilirubin $> 2 \times \text{ULN}$

11.4 Analysis of Vital Signs and Weight

11.4.1 Variables and Criteria Defining Abnormality

The following vital sign parameters will be assessed: Systolic blood pressure [mmHg], Diastolic blood pressure [mmHg], Pulse [beats per minute], Respiratory rate [breaths per minute], Temperature [$^{\circ}\text{C}$], Weight [kg]. The following [Table 16](#) presents the Criteria for Potentially Clinically Important Vital Sign Findings. Of note, a post baseline value must be more extreme than the baseline value to be considered a potentially clinically important finding.

Table 16. Criteria for Potentially Clinically Important Vital Sign Findings

Vital Sign	Category	Criteria for Potential Clinically Important Vital Signs
Systolic Blood Pressure	Low Value	≤ 90 mmHg and decrease ≥ 20 mmHg from Baseline
	High Value	≥ 160 mmHg and increase ≥ 20 mmHg from Baseline
Diastolic Blood Pressure	Low Value	≤ 50 mmHg and decrease ≥ 10 mmHg from Baseline
	High Value	≥ 100 mmHg and increase ≥ 10 mmHg from Baseline

11.4.2 Statistical Methods

Changes from Baseline to each visit and to the final value in vital sign parameters will be summarized with the mean, standard deviation and median. The Baseline and final value means will also be presented for subjects who have both the Baseline and final values.

For baseline, if there are multiple measurements on the same day, the last measurement prior to the first dose of study drug will be used as the Baseline vital sign value. If there are multiple post-baseline measurements on the same day, average value will be used.

For systolic blood pressure and diastolic blood pressure, a listing of all subjects with any vital sign value meeting criteria for potentially clinically important values will be provided. For each of these subjects, the whole course of the respective parameter will be listed. The number and percentage of subjects who have at least one value meeting criteria for potentially clinically important values will be provided for each selected vital sign parameter.

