The subject's demographic data, including date of birth, gender, race, ethnicity, and disease status that has been collected at the screening visit of the preceding study will be used in Study M15-997, so does not need to be collected again.

Medical and Surgical History

Medical history collected in the preceding study will be used in Study M15-997. Only new information and updates will need to be collected at the Study M15-997 Baseline Visit.

Physical Examination

Symptom directed physical examination will be performed at visits as described in [Appendix C](#). Clinically relevant abnormal findings will be reported as medical history or AEs.

Vital Signs Assessment

Vital signs assessments include temperature, pulse rate, sitting blood pressure, and respiratory rate, after subjects have been seated comfortably for at least 5 minutes.

Measurement of vital signs must precede blood sampling and be assessed pre-dose at all dosing visits.

Additional vital signs assessments should be made 5 (\pm 2) minutes post-dose and 60 (\pm 10) minutes post-dose at Visit 1 and Visit 2.

Body Weight

Body weight measurements should be done on the same scale for each subject, as possible. In order to get comparable body weight values, body weight measurements should be performed in the following manner:

- after the urine sampling (body weight after bladder voiding)
- shoes and coat/jackets should be taken off
- pockets should be emptied of heavy objects (i.e., keys, coins etc.)

12-Lead Electrocardiogram (ECG)

The 12-lead ECGs will be performed as scheduled in [Appendix C](#).

ECGs will be recorded after the subject has rested for at least 5 minutes in a supine position and will always precede blood sampling. Six limb leads, as specified by

Einthoven (I, II and III) and Goldberger (aVR, aVL, aVF), and six pre-cordial leads (V1 – V6), according to Wilson, will be used.

ECGs may be repeated for quality reasons and the repeat used for analysis. Additional ECGs may be collected for safety reasons. Clinically relevant, abnormal findings will be reported as AEs.

Dated and signed printouts will be stored in the subject's medical file.

In the event a scheduled ECG may not be performed due to study modifications related to the COVID-19 pandemic, perform the 12-lead ECG at the next earliest feasible visit or arrange to have an alternative acceptable local facility perform the ECG for the subject.

Psoriasis Area and Severity Index (PASI) Evaluation

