b. Premature discontinuation: For subjects who prematurely discontinue the study before study end (for any reason) an early EOT visit is required.

If the decision to discontinue study participation is made at a regular study visit, the visit should be turned into an EOT visit, i.e., an EOT visit is to be performed instead of the scheduled visit.

If the decision to discontinue study participation is made in between study visits, an EOT visit is to be scheduled at the earliest convenience or at the latest the next upcoming visit according to the Flow Chart. This early EOT visit will include the same procedures as the normal EOT visit and the subject will subsequently enter a follow up period of 20 weeks, until a final EOO visit is performed.

- c. Informed consent must not be signed before the date of the last visit in the preceding study, but needs to be completed prior to initiation of any Study M15-997 study procedures.
- d. The subject's demographic data has been collected at the screening visit of the preceding study, so does not need to be collected again.
- e. Medical history collected in the preceding study will be used in Study M15-997. Only new information and updates will need to be collected at the Study M15-997 Baseline visit.
- f. For subjects rolling over from the preceding study with ≤ 4 day delay from the last visit per protocol in the preceding study, these procedures do not need to be repeated if already performed at this last visit of the preceding study. Results assessed at this last visit will serve as Baseline visit results for Study M15-997. Subjects initiating the OLE with a delay of > 4 days from completion of the last visit per protocol in the preceding study will need to complete all activities for Baseline.
- g. New Adverse Events or unresolved Adverse Events from the preceding study to be followed up in this study.
- h. Symptom directed physical exam.
- i. Vital Signs must precede blood sampling and must be assessed pre-dose at all dosing visits. Additional vital signs assessments should be made 5 (± 2) minutes post-dose and 60 (± 10) minutes post-dose at Visit 1 and Visit 2.
- j. Only subjects that had a negative TB test during the last testing in the preceding study or Study M15-997 will be tested for TB.
- k. Urine pregnancy testing at every dosing visit. Additional serum pregnancy testing will occur in case of a positive urine test result at any visit.

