6.0 Analysis Conventions

Since this is an open-label continuation study, no statistical test will be conducted. Summary statistics will be provided. Data from preceding studies will be integrated with data from this study in the summaries.

Definition of Baseline

For this study, the following two types of baseline values are defined.

1. Preceding Study Baseline Value (BL): These values represent the baseline values of preceding studies, that is, the last non-missing values on or before the date of the first dose of study drug in the preceding study. For vital sign assessments, only assessments prior to first dose time will be considered, since vital signs are to be assessed both pre- and post-dose in some visits. The efficacy analysis based on RZB, RZB_NL, Retreatment, UST_RZB, ADA_RZB, FUM_RZB, and RZB_Japan populations will use these baseline values. These baseline values will be referred to as "BL" in this document. Unless otherwise specified, this will be the "baseline" for analysis.
2. RZB baseline value (BL_RZB): These values are the last non-missing values on or before the date of the first dose of risankizumab in the preceding study or Study M15-997. For vital sign assessments, only assessments prior to first dose time will be considered, since vital signs are to be assessed both pre- and post-dose in some visits. These values will be referred to as BL_RZB in this document. BL_RZB will be used for safety analyses in all populations.

Definition of Final Observation (Applicable to Safety Analyses)

Final observation in the entire study is defined as the last non-missing observation collected within 140 days after the last dose of risankizumab.

Definition of Rx Days (Days Relative to the Date of First Dose of Study Drug)

Rx days are calculated for each time point relative to the date of first dose of risankizumab in the corresponding study period. They are defined as the number of days between the day of the first dose of risankizumab and the specific time point. Rx days are negative values when the time point of interest is prior to the first risankizumab dose day. Rx days are positive values when the time point of interest is on or after the first risankizumab dose day. The day of the first dose of risankizumab is defined as Rx Day 1, while the day prior to the first risankizumab dose is defined as Rx Day -1 (there is no Rx Day 0).

Definition of Analysis Windows

All time points and corresponding time windows are defined based on Rx Days.

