For efficacy analyses, local tolerability, laboratory parameters, and vital sign variables, analysis windows are constructed using the following algorithm:

- Determine the nominal Rx day for each visit (e.g., Week 4 [4 weeks after Baseline visit] equals Rx Day 29).
- In order to include all post baseline data, the first post-baseline interval starts on the first day after the first dose of risankizumab (Rx Day 2).
- Determine the window around a specific nominal Rx day by adding or subtracting half of the interval between adjacent visits (e.g., days between Week 2 and Week 4 is 14). The threshold between adjacent visits is determined by splitting the interval evenly between the visits. If the resulting split is between Rx days, then the threshold is determined as the midpoint between the adjacent visits. If the resulting split is on an Rx day, then the threshold is determined as being between that Rx day and the Rx day prior to it (e.g., the split between Week 2 and Week 4 would be between Rx Days 22 and 23).
- If more than one assessment is included in a time window the assessment closest to the nominal day will be used. If there are two observations

equidistant to the nominal day, the one after the nominal day will be used in analyses. If more than one post baseline assessment is included on the same day, then the worst assessment on that day will be used in analyses, except those specified in Section 11.0.

The protocol specified visits and corresponding time windows used in the efficacy analyses, local tolerability, laboratory parameters, and vital sign variables, are presented in the following tables.

Table 1. Visit Windows for Analysis of PASI, sPGA, Local Tolerability Assessment, Clinical Laboratory Tests, and Vital Signs (RZB Population)

Window Label	Target Day	Interval
Baseline ^a	1	≤ 1 ^b
Week 4	29	[2, 43]
Week 8	57	[44, 71]
Week 12	85	[72, 99]
Week 16	113	[100, 155]
Week 28	197	[156, 239]
Week 40	281	[240, 323]
Week 52	365	[324, 407]
Week 64	449	[408, 491]
Week 76	533	[492, 575]
Week 88	617	[576, 659]
Week 100	701	[660, 743]
Week 112	785	[744, 827]
Week 124	869	[828, 911]
Week 136	953	[912, 995]
Week 148	1037	[996, 1079]
Week 160	1121	[1080, 1163]
Week 172	1205	[1164, 1247]
Week 184	1289	[1248, 1331]
Week 196	1373	[1332, 1415]
Week 208	1457	[1416, 1541]
Week 232	1625	[1542, 1709]
Week 256	1793	[1710, 1877]
Week 280	1961	[1878, 2045]
Week 304	2129	[2046, 2199]

a. There is no baseline for local tolerability measurements.

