Week 84	589	[548, 631]
Week 96	673	[632, 715]
Week 108	757	[716, 799]
Week 120	841	[800, 883]
Week 132	925	[884, 967]
Week 144	1009	[968, 1051]
Week 156	1093	[1052, 1177]
Week 180	1261	[1178, 1345]
Week 204	1429	[1346, 1513]
Week 228	1597	[1514, 1681]
Week 252	1765	[1682, 1835]

a. If time is collected in vital signs, restrict to records prior to the first dose of RZB in Study M15-997.

Note: Rx Day calculated relative to first dose date of risankizumab.

Table 11. Visit Windows for Analysis of NAPSI, PPASI, PSSI, and DLQI (UST_RZB, FUM_RZB, RZB_Japan Populations)

Window Label	Target Day	Interval
Entry of Study M15-997	1	≤ 1
Week 24	169	[2, 253]
Week 48	337	[254, 421]
Week 72	505	[422, 589]
Week 96	673	[590, 715]
Week 108	757	[716, 799]
Week 120	841	[800, 925]
Week 144	1009	[926, 1051]
Week 156	1093	[1052, 1177]
Week 180	1261	[1178, 1345]
Week 204	1429	[1346, 1513]
Week 228	1597	[1514, 1681]
Week 252	1765	[1682, 1835]

Note: Rx Day calculated relative to first dose date of risankizumab.

Definition of Missing Data Imputation

No global imputation is taking place at the database level. Efficacy related imputations are outlined in Section 10.0. There is no imputation for missing values in the safety analyses.

Rounding of Numeric Results

Rounding will be performed for presentation of results. No rounding will be performed before or during analyses. The ROUND function of SAS will be used to round results.

When dichotomizing continuous variables, associated continuous variables will be rounded to 9 decimal points before applying the cutoff point to determine the response status (for example, percent change from baseline in PASI score will be rounded to 9 decimal places before comparing to 90%).

The mean and median will be rounded for presentation to 1 decimal more than the data entered into the database. The standard deviation will be rounded to 2 decimal places more than the data entered into the database. The minimum and maximum values will be presented as entered into the database.

Probabilities will be rounded to 3 decimal places before assignment of statistical significance and will be presented in rounded format. Probabilities that round to zero or are reported by SAS as zero will be presented as "< 0.001." Probabilities that round to 1 or are reported by SAS as 1 will be presented as "> 0.999."

7.0 Demographics, Baseline Characteristics, Medical History, and Previous/Concomitant Medications

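### By-visit vital signs in the SAP average post-dose readings with the pre-dose reading, or leave them outside every window, so no described output shows post-dose change at Visits 1 and 2

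*SAP*

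**What the plan says.** **Collection.** Protocol Appendix C, in line with Section 5.3.1.1, requires a pre-dose assessment at every dosing visit and adds: "Additional vital signs assessments should be made 5 (± 2) minutes post-dose and 60 (± 10) minutes post-dose at Visit 1 and Visit 2". No other scheduled M15-997 visit has post-dose readings.

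**Baseline.** SAP 6.0 limits the vital-sign baseline to readings before the first dose: "only assessments prior to first dose time will be considered, since vital signs are to be assessed both pre- and post-dose in some visits". The authors therefore knew that some visits carry both kinds of reading.

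**Same-day rule.** The general rule in SAP 6.0 for several post-baseline assessments on one day is: "then the worst assessment on that day will be used in analyses, except those specified in Section 11.0". SAP 11.4.2 uses that exception for vital signs: "If there are multiple post-baseline measurements on the same day, average value will be used".

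**Windows.** In SAP 6.0, "the first post-baseline interval starts on the first day after the first dose of risankizumab (Rx Day 2"). For the Day 1 row of Table 10, where vital-sign times are collected, footnote a says to "restrict to records prior to the first dose of RZB in Study M15-997". Table 8 has a matching footnote for ADA_RZB.

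**Outputs.** SAP 11.1 plans change from baseline in vital signs for RZB, RZB_NL, UST_RZB, ADA_RZB, FUM_RZB and RZB Japan. It plans potentially-clinically-important summaries for all populations. Table 16 gives such criteria for systolic and diastolic blood pressure only.

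**The concern.** The SAP uses the pre-dose/post-dose distinction to define baseline and then drops it. It defines no post-dose time point and no change from pre-dose to post-dose. What happens to a reading taken minutes after injection depends only on whether that day is Rx Day 1 for the subject. If it is, the reading belongs to no window. If it is not, it is averaged with the pre-dose reading.

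This has two consequences. The mean change at the windows holding Visits 1 and 2 mixes readings of different kinds, so it is not like-for-like with the pre-dose values at later M15-997 visits. And any acute shift is shrunk or absent in the by-visit tables. For pulse, respiratory rate and temperature the SAP gives no threshold criteria that would pick it up elsewhere. The primary objective is long-term safety and tolerability, so data that the protocol requires should be reported in a form that can be interpreted.

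**Working it through.** The plan states no figure on this point, so there is nothing to reproduce. The check follows each reading through the windows and then works out the average.

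**Step 1: where the readings go.** The Visit 1 days for subjects already on risankizumab are assumptions; any day after Rx Day 1 gives the same outcome. Visit 2 is 84 days after Visit 1.

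| Subjects | Visit 1 day | Visit 1 post-dose readings | Visit 2 day | Visit 2 readings |
|---|---|---|---|---|
| UST_RZB, FUM_RZB (Table 10); ADA_RZB switching at OLE (Table 8) | 1 | no window: Day 1 row is pre-dose only, next window is [2, 127] | 85 | Week 12 or 12S, pre- and post-dose together |
| RZB (Table 1) | 365, assumed | Week 52 [324, 407], with any same-day pre-dose reading | 449 | Week 64 [408, 491], together |
| RZB_NL (Table 3) | 253, assumed | Week 36S [212, 295], likewise | 337 | Week 48S [296, 379], together |
| ADA_RZB switching at Week 16 (Table 8) | 197, assumed | Week 28S [184, 239], likewise | 281 | Week 40S [240, 323], together |

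The Day 1 footnotes apply only if time is collected, but the baseline definitions in SAP 6.0 and 11.4.2 exclude post-dose readings in any case. RZB Japan is ambiguous. Table 10's row label and footnote point to entry into M15-997, while its note counts from the first risankizumab dose. For previously treated Japanese subjects the Visit 1 post-dose readings are lost on one reading and averaged on the other.

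**Step 2: what averaging does.** Let the pre-dose reading be p, the changes from it d5 and d60, and all three readings fall on one day:

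- visit value = (p + (p + d5) + (p + d60))/3 = p + (d5 + d60)/3
- change at one post-dose reading only: d/3
- the same change at both: 2d/3

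Illustrative systolic values in mmHg (not from the documents), with the pre-dose value equal to baseline:

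- 110, 80, 110: mean 300/3 = 100. A fall of 30 is reported as 10.
- 120, 88, 118: mean 326/3 = 108.7. A fall of 32 is reported as 11.3.
- 120, 88, 88: mean 296/3 = 98.7. A fall of 32 is reported as 21.3.

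**Step 3: when d/3 does not apply.** Appendix C footnote f lets a subject who rolls over within 4 days reuse the vital signs from the last visit of the preceding study. The Visit 1 pre-dose reading may then be on another day. The Visit 1 same-day average would cover the two post-dose readings alone, and a change at one of them enters as (d + 0)/2 = d/2, provided that day is the one selected for the window. Visit 2 is unaffected by this.

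**Step 4: the threshold output.** Table 16 flags a low systolic value at 90 mmHg or less with a fall of at least 20 mmHg. In the second example 88 with a fall of 32 qualifies; the average of 108.7 with a fall of 11.3 does not. So the order of averaging and flagging decides the result. SAP 11.3.2 gives both rules for laboratory data: the average for change from baseline and the worst value in its text on important values. SAP 11.4.2 gives only the average. Table 16 also needs a post-baseline value, and the SAP does not say whether a reading taken after the dose on Rx Day 1 counts as one.

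**The case against.** The strongest reply is that averaging is a deliberate, stated choice in a study with no hypothesis tests, and that a table of mean change is not where acute reactions are sought. Much of this stands.

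- **Detection.** A reader might infer that acute reactions would go unnoticed. The documents do not support that. Protocol 5.3.1.1 provides post-dose observation of about 2 hours at Baseline and about 1 hour at later visits, a supplemental form and blinded adjudication of suspected anaphylaxis. SAP 11.2.1 treats events starting on the dosing day as treatment-emergent unless they began before the dose, and Table 12 covers hypersensitivity and adjudicated anaphylaxis. The protocol also gives no purpose for the 5- and 60-minute readings, so calling them an acute-reaction screen would be inference.
- **Blood pressure extremes.** SAP 11.4.2 lists subjects with any qualifying value and shows the full course of the parameter. That wording favours individual readings, so the 88 mmHg in the example would probably be flagged.
- **Scope.** A reader might infer that all four post-dose readings of every subject are mishandled. By-visit change is planned for six populations only. Retreatment and ALL_RZB have no such table, and subjects from 1311.13, for example, are in none of the six unless they are from Japan. First exposure at Visit 1 concerns only UST_RZB, FUM_RZB and OLE-switching ADA_RZB.
- **Comparability.** The contrast with pre-dose-only visits holds for scheduled M15-997 visits. Vital-sign schedules in the preceding studies are not in these documents.
- **Windows.** Opening the first window to Rx Day 1 would not help: the reading closest to target is used, so Visit 2 at Day 85 would displace it.
- **Outputs.** SAP 17.0 leaves the full output list to a separate document. One can say only that the SAP describes no post-dose table.

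The reply does not defend one visit value that combines pre- and post-dose readings, and it points to no threshold criteria for pulse, respiratory rate or temperature.

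**Conclusion.** The point holds as a minor reporting defect. In the six populations with planned by-visit change, the stated rule produces a mixed value at Visit 2, and at Visit 1 for subjects already on risankizumab. It reduces a single-reading change to one third when all three readings share a day. For UST_RZB, FUM_RZB and OLE-switching ADA_RZB subjects, the two Visit 1 post-dose readings appear in no by-visit summary.

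No effect on population means can be estimated, because the documents give no post-dose data. The size given here is the per-subject attenuation. It rests on same-day readings and on taking Visit 1 as Rx Day 1 in the three groups just named, as Tables 8 and 10 label it. Whether the blood pressure listing is also affected is open: the wording suggests not, but the SAP does not settle it.

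**What to change.** Change SAP 11.4.2 in three places:

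1. For change from baseline at M15-997 visits, take the last pre-dose reading as the visit value. Say that a reading carried over from the preceding study under Appendix C footnote f counts as the Visit 1 pre-dose reading.
2. Add one descriptive table of change from pre-dose to 5 and to 60 minutes post-dose at Visits 1 and 2, for each vital sign and for each of the six populations. This gives the Rx Day 1 post-dose readings a place without altering the windows.
3. State that Table 16 applies to individual, unaveraged readings, including those taken after the dose on Rx Day 1.

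The cost is a few lines of SAP text and one extra descriptive table from data already collected. No study procedure changes.
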